6.4.3 Secondary Efficacy Analyses

The following secondary endpoints will be summarized, overall and by weight group ($\leq 40, > 40$ kg):

- The LV peak contrast intensity, determined as None, Low, Medium, High or Blooming, will be summarized as a categorical variable for each OPTISON dose level.

- The peak LV contrast filling, categorized as None (0% filling), Faint (around 33% filling), Intermediate (around 67% filling) or Full (100% filling), will be summarized as a categorical variable for each OPTISON dose level.
- The contrast enhancement duration in the LV chamber determined from the time contrast appears in the LV to the time it almost dissipates from the chamber as determined by investigators, will be summarized with descriptive statistics for each OPTISON dose level.
- Image quality, categorized as Excellent/good, Adequate or Poor will be summarized as a categorical variable for each OPTISON dose levels.
- Diagnostic usefulness, evaluated as Non-diagnostic (the image quality is not sufficient to confidently visualize the endocardial border) or Diagnostic (sufficient or excellent image quality for EBD assessments), will be summarized as a categorical variable for non-contrast and OPTISON dose levels.
- The diagnostic confidence of the assessment of LV EBD and wall motion, assessed using a 4-point scale (0 = no confidence, 1 = low confidence, 2 = moderate confidence, 3 = high confidence) will be described for non-contrast and OPTISON dose levels.

The change in diagnostic confidence will be derived by comparing non-contrast and OPTISON-enhanced diagnostic confidence scores as follows (contrast-enhanced minus unenhanced):

- ≤ -1 = confidence is lower with contrast-enhanced images
- 0 = confidence is the same between unenhanced and contrast-enhanced images
- 1 = confidence is slightly improved with contrast-enhanced images
- 2 = confidence is moderately improved with contrast-enhanced images
- 3 = confidence is greatly improved with contrast-enhanced images.

Diagnostic confidence in comparison to non-contrast echocardiographic images will be summarized as a categorical variable by OPTISON dose level.

- The diagnostic confidence of the evaluation of LVEF, assessed using a 4-point scale (0 = no confidence, 1 = low confidence, 2 = moderate confidence, 3 = high confidence) will be described for non-contrast and OPTISON dose levels.

The change in diagnostic confidence will be derived using the same method as for change diagnostic confidence of the assessment of LV EBD and wall motion and summarized as a categorical variable by OPTISON dose level.

- LV function assessed by LVEFs, calculated using the formula: (end diastolic volume – end systolic volume)/end diastolic volume for each ventricle, will be summarized with descriptive statistics for non-contrast and OPTISON dose levels
- A composite assessment of dose suitability will be made at the subject level and results will be tabulated by OPTISON dose level. A dose will be considered suitable if it meets the following criteria:
 - (1) There is an increase in the number of segments adequately visualized over non-contrast images
 - (2) LVO peak contrast intensity assessed as medium or better
 - (3) Peak LV contrast filling to around 67% or better
 - (4) Duration of contrast enhancement ≥ 1.5 minutes.

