Study Design: This will be a Phase 4, open-label, non-randomized, multi-center, multi-dose study in North America and Europe. The study is designed to evaluate overall efficacy and safety of intravenous administration of OPTISON at various doses in pediatric patients undergoing transthoracic echocardiography. Approximately 50 pediatric patients between ≥ 9 and <18 years of age weighing ≥ 20 kg who are clinically indicated for a transthoracic echocardiogram and are likely to have a limited transthoracic echocardiographic window based on body habitus and/or previous cardiac operation or have a previous suboptimal non-contrast echocardiogram will be enrolled into the study. OPTISON will be administered according to pediatric body weight (≥ 20 to ≤ 28 kg, >28 to ≤ 40 kg, and >40 kg). Each subject will receive administrations of 2 different dose levels. Injections should be at least 10 minutes apart between the 2 dose levels to allow for clearance of the previous dose. For echocardiographic imaging, standard apical 4-chamber and 2-chamber views will be obtained at baseline using tissue harmonic imaging, thereafter with contrast using a contrast-imaging mode. Additional views may be obtained at the clinician's discretion. All image views will be obtained prior to and after contrast administration until 10 minutes post injection. All images will be recorded on disk and sent to image core lab for preparation of blinded image evaluation (BIE). Efficacy assessment will be based on the results of the BIE. Clinical safety data will be collected throughout the study, beginning at baseline throughout 72 hours post OPTISON administration.		
Primary Endpoint:		

Visualization of the 12 segments of the left ventricle wall in standard apical 4-chamber and 2-chamber views measured by the qualitative EBD visualization scale.		
Secondary Endpoints:		

Overall safety profile in terms of occurrence of adverse events (AEs) and changes in vital signs, arterial oxygen saturation (SaO_2), physical examinations and 12-lead electrocardiograms (ECGs) following administration of different OPTISON doses in pediatric patients.		

Name of Sponsor/Company: GE Healthcare Ltd. and its Affiliates	Individual Study Table Referring to Part of Dossier in Which the Individual Study or Study Table is Presented:	(For National Authority Use Only)
Name of Finished Product: OPTISON™		

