10.2 Efficacy Assessment

Efficacy will be assessed by 3 independent blinded readers unaffiliated with enrolling centers and based on characteristics of LV EBD, LVO, diagnostic confidence for the assessment of LV EBD and wall motion, and for the evaluation of LVEF for both non-contrast and CE-ECHO.

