10.2.4 Image Interpretation

All echocardiographic images will be evaluated by 3 independent blinded readers for characteristics of LV EBD, LVO, diagnostic confidence for the assessment of LV EBD and wall motion, and for the evaluation of LVEF. The BIE process is described in detail in the Independent Review Charter.

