12.3.2 Secondary Efficacy Analysis

The following secondary endpoints will be summarized:

- The LV peak contrast intensity, determined as none, low, medium, high or blooming, will be summarized as a categorical variable by OPTISON dose level.
- The peak LV contrast filling, determined as none, faint, intermediate or full, will be summarized as a categorical variable by OPTISON dose level.
- The contrast enhancement duration in the LV chamber determined from the time contrast appears in the LV to the time it almost dissipates from the chamber as determined by investigators, will be summarized with descriptive statistics by OPTISON dose level.
- Image quality, categorized as excellent/good, adequate or poor will be summarized as a categorical variable for OPTISON dose levels.
- Diagnostic usefulness, evaluated as non-diagnostic or diagnostic, will be summarized as a categorical variable for non-contrast and OPTISON dose levels.

- The diagnostic confidence of the assessment of LV EBD and wall motion, assessed using a 5-point scale in comparison to non-contrast echocardiographic images (confidence was lower with contrast-enhanced images, same between unenhanced and contrast-enhanced images, slightly improved with contrast-enhanced images, moderately improved, greatly improved), will be summarized as a categorical variable by OPTISON dose level.
- The diagnostic confidence of the evaluation of LVEF, assessed using a 5-point scale in comparison to non-contrast echocardiographic images (confidence was lower with contrast-enhanced images, same between unenhanced and contrast-enhanced images, slightly improved with contrast-enhanced images, moderately improved, greatly improved), will be summarized as a categorical variable by OPTISON dose level.
- LV function assessed by LVEFs, calculated using the formula: (end diastole volume – end systole volume)/end diastole volume for each ventricle, will be summarized with descriptive statistics by OPTISON dose levels and compared with non-contrast images.

A composite assessment of dose suitability will be made at the subject level and results will be tabulated by OPTISON dose level. A dose will be considered suitable if it meets the following criteria:

- (1) There is an increase in the number of segments adequately visualized over non-contrast images
- (2) LVO peak contrast intensity assessed as medium or better
- (3) Peak LV contrast filling to around 67% or better
- (4) Duration of contrast enhancement ≥ 1.5 minutes

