1. Evaluation of Left ventricular (LV) Endocardial Border Delineation (EBD)
2. Evaluation of diagnostic confidence for the assessment of LV EBD and wall motion
3. Evaluation of Left Ventricular Opacification (LVO)
4. Evaluation of Image Quality and Diagnostic Usefulness
5. Evaluation of Left Ventricular Function
6. Evaluation of diagnostic confidence for the assessment of LVEF
7. Evaluation of Duration of Contrast Enhancement.

Clinical safety data will be collected throughout the study, beginning from dosing through 72 hours post OPTISON administration to determine the safety profile of intravenous administration of OPTISON at various doses in pediatric population.

Figure 1 Study Diagram

All efficacy and safety measurements obtained during the course of the study are summarized in the Study Schedule of Events ([Table 2](#)).

Table 2 Study Schedule of Events

Variables	Pre-procedure		Dosing/ Imaging (0)	Post-last OPTISON Administration				
	Screening (≤2 weeks)	Baseline (from -1 ± 1 h)		10 min (±5 min)	30 min (±5 min)	1 h (±5 min)	24 h (±4 h)	72 h (±8 h)
Informed Consent	X							
Entry Criteria	< ----- >							
Demographic Information	X							
Medical/Surgical History	X							
Pregnancy test ^a	X	X						
Physical Examination		X				X		
Vital Signs		X		X		X		
SaO ₂ by Pulse Oximetry		X	X	X		X		
12-Lead ECG Recording		X		X	X			
Prior and concomitant Medications ^b		< ----- >						
Continuous ECG Monitoring ^c			< ----- >					
OPTISON Administration			X					
Image Acquisition		X	X					
Phone Calls							X	X
AEs and SAEs Monitoring	X	<----->						

AE = Adverse event; ECG = Electrocardiogram; SAE = Serious adverse event; SaO₂ = Oxygen saturation

a Urine β-hCG pregnancy test at screening and at pre-dose; post-menarchal females only.

b Any prior or concomitant medication taken by the subject within 24 hours before OPTISON injection and up to the end of the 72-hour follow-up period.

c Continuous ECG monitoring is from time of first OPTISON injection until 30 minutes after the last OPTISON injection

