6.4 Efficacy Analysis

6.4.1 General Considerations

Since this is a dose-finding study, no hypotheses are being tested. All efficacy results will be summarized for the FAS and PP populations.

Assessments to be used for image interpretation are identified by the site and recorded in the eCRF. These identified assessments will be used for efficacy analyses.

Efficacy summaries will be presented for each reader.

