6.4.5 Reader Differences

All efficacy summaries described in Section 6.4 will be presented by reader.

Data from re-read will be listed.

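### The plan conflicts on whether open-label investigators or blinded readers determine contrast enhancement duration, which feeds criterion (4) of the dose-suitability composite

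*SAP*

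**What the plan says.** Two analysis sections give the assessment of duration to site staff. SAP 6.4.3 has it end when "it almost dissipates from the chamber as determined by investigators, will be summarized with descriptive statistics for each OPTISON dose level". Protocol 12.3.2 has the same phrase: "it almost dissipates from the chamber as determined by investigators".

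Other sections of both documents point to the blinded readers:

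- Protocol synopsis, Study Design: "Efficacy assessment will be based on the results of the BIE".
- Protocol 10.2: "Efficacy will be assessed by 3 independent blinded readers unaffiliated with enrolling centers".
- Protocol 10.2.4: "All echocardiographic images will be evaluated by 3 independent blinded readers for characteristics of LV EBD, LVO". Protocol 10.1.2 makes duration part of the LVO endpoint.
- SAP 2.2, in the list of analyses under the independent review charter: "7. Evaluation of Duration of Contrast Enhancement".
- SAP 6.4.1: "Efficacy summaries will be presented for each reader". SAP 6.4.5: "All efficacy summaries described in Section 6.4 will be presented by reader". Section 6.4 contains both the duration summary and the composite.

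The composite in SAP 6.4.3 (protocol 12.3.2) calls a dose suitable for a subject when four criteria are met: more segments visualized than without contrast, peak intensity of medium or better, filling of around 67% or better, and duration of at least 1.5 minutes.

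**The concern.** The duration summary and criterion (4) have two possible sources under the text as written. One is a single site value per dose from someone who knows the dose, because the study is open-label (SAP 2.5) and the two levels are given in ascending order (protocol synopsis). The other is three values from readers who have no dosing information. The end of the interval, when contrast has almost gone, is a judgement, so knowledge of the dose can influence it.

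If the site value is used, criterion (4) is identical in all three by-reader composites, while criteria (1) to (3) can differ by reader. Each reader's composite would then mix one dose-aware input with three blinded ones. The composite supports the choice of dose, and duration is also named directly in the dose-selection rule at the end of protocol 10.2.1.

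**Working it through.** **1. Can the documents settle the assessor?**

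| Place | Assessor of duration |
|---|---|
| SAP 6.4.3; protocol 12.3.2 | Investigators |
| SAP 2.2, item 7 of the charter analyses | Blinded read |
| Protocol synopsis, Efficacy Evaluation | Blinded readers evaluate the images; duration is listed beneath, under LVO |
| Protocol 10.1.2 with 10.2.4 | Duration belongs to LVO; blinded readers evaluate LVO |
| SAP 6.4.1 and 6.4.5 | Summaries by reader |
| SAP 6.4.4 | Uninterpretable images count as zero duration, which fits an image-read variable |
| Protocol Table 3 | Names blinded readers for peak intensity, no assessor for duration |

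SAP 1 lets the SAP prevail over the protocol. That does not help, because SAP 6.4.3 disagrees with SAP 2.2 and 6.4.5. The table of changes in SAP 9 does not mention duration.

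**2. The plan's own figure for this endpoint.** SAP 2.3 (protocol 12.5) bases its power table on duration: paired t-test, one-sided alpha 0.025, mean difference 0.7 min, SD of the difference 1.5 min. Exact power is the probability that a noncentral t with n − 1 degrees of freedom and noncentrality (0.7/1.5)·√n exceeds the 0.975 quantile of the central t.

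| n | 30 | 40 | 50 | 60 | 70 | 80 |
|---|---|---|---|---|---|---|
| Stated (%) | 70 | 82 | 90 | 94 | 97 | 98 |
| Recomputed (%) | 69.5 | 82.1 | 89.9 | 94.5 | 97.1 | 98.5 |

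The table reproduces within a point. Naming the assessor changes none of these figures.

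**3. Illustration of what a dose-aware reading could do to criterion (4).**

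Inputs from the documents:
- cut-off 1.5 min (SAP 6.4.3);
- 30 evaluable subjects (SAP 2.3);
- durations of up to 60 seconds in one pediatric study and 2.5 to 4.5 min in adults (protocol 6.2.1), used to set the range of means.

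Assumptions not in the documents:
- a lean of b = 0.25 min at the higher dose;
- normally distributed durations;
- a per-dose SD of 1.06 to 1.5 min. The lower value is 1.5/√2 = 1.06, the planning SD of the difference if the two doses are uncorrelated with equal variances.

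The share of subjects moved across the cut-off is Φ((m + b − 1.5)/SD) − Φ((m − 1.5)/SD). For example, with m = 1.5 and SD = 1.06 it is Φ(0.236) − Φ(0) = 0.593 − 0.500 = 9.3 points, and 0.093 × 30 = 2.8 children.

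| Mean m (min) | Shift, SD 1.06 (points) | Shift, SD 1.5 (points) | Children of 30 (SD 1.06 / 1.5) |
|---|---|---|---|
| 1.0 | 8.8 | 6.4 | 2.6 / 1.9 |
| 1.5 | 9.3 | 6.6 | 2.8 / 2.0 |
| 2.5 | 5.4 | 5.0 | 1.6 / 1.5 |
| 3.5 | 1.3 | 2.4 | 0.4 / 0.7 |
| 4.5 | 0.1 | 0.8 | 0.04 / 0.2 |

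The effect on the composite is equal or smaller, because a child who fails any of criteria (1) to (3) keeps the same status.

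**The case against.** The best counter-argument is that the second source may not exist. Protocol 9.3 lists what sites record at dosing (volumes, number of boluses, safety data) and includes no timing of contrast. The schedule of events shows image acquisition only. SAP 6.4.1 gives the site the task of identifying which assessment is used for interpretation. The programmed listings in SAP 8 include the blinded interpretations but no investigator duration. Against all the places that imply a reader, a single phrase points the other way, in near-identical wording in two sections, and it may be loose wording for the readers. Table 3's silence is also weak evidence, since it names no assessor for filling either.

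This makes the blinded reading the more likely intention. It does not remove the conflict. The documents otherwise use the word for site staff and call the image assessors readers, the case report form was not available to rule out a duration field, and in the SAP 6.4.3 list only the duration bullet names an assessor.

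The objection to the numbers is fair. The 0.25-minute lean has no basis in the documents. The 60-second figure is an upper limit for adequate opacification, so it is neither a mean nor the same interval. At a mean of 1.0 min the normal model gives 17% to 25% of children a negative duration (8% to 16% at 1.5 min). The table therefore shows only how sensitive the cut-off is and does not estimate bias.

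**Conclusion.** The concern holds. The SAP contradicts itself on who determines duration, and neither the precedence rule nor the table of changes resolves it. It should be fixed before the analysis is programmed.

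The stakes are limited. Protocol 10.2.1 bases the dose choice primarily on segment improvement, with duration supplementary, and duration has only a descriptive summary. The primary EBD endpoint and the planned paired t-tests are unaffected.

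The effect is zero if the word means the blinded readers. If it is meant literally, the size depends on the assumed lean and on where durations fall. Under the assumptions above it is about 2 to 3 of 30 children at means of 1.0 to 1.5 min, about 1.5 at 2.5 min, and fewer than 1 at 3.5 min or more. The Independent Review Charter, which probably settles the intention, is a separate document and was not seen.

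**What to change.** 1. Check in the Independent Review Charter that the duration item is read by the blinded readers.
2. In SAP 6.4.3 and protocol 12.3.2, replace the reference to investigators with each blinded reader in the blinded image evaluation. Name the same assessor for duration in protocol Table 3.
3. State in SAP 6.4.3 that criterion (4) in each reader's composite uses that reader's own duration. SAP 6.4.5 already requires the composite by reader but does not say whose duration enters it.
4. If the site does record a duration, present it as supportive only.

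The cost is wording alone if the charter already has duration as a blinded read. If it does not, blinded timing has to be added on images already collected: about 30 subjects × 2 dose levels × 3 readers = 180 readings.

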6.2.1 Justification of Dose Selection and Efficacy Analysis

In the adult controlled clinical trials for the LVO and EBD indication, the duration of the useful imaging time for LV chamber opacification was 2.5 to 4.5 minutes for a dose of 0.5 to 3.0 mL [OPTISON PI].

McMahon et al conducted rest non-contrast and CE-ECHO in 20 children (9 to 18 years) with limited transthoracic echo windows [McMahon et al. 2005]. OPTISON was administered at a dose of 0.3 mL per injection for children <20 kg and 0.5 mL per injection for those ≥ 20 kg. The EBD was significantly improved in all patients with CE-ECHO and LVEF was measurable in all 20 patients using contrast echo versus only 11 with non-contrast echocardiography. Zilberman et al performed contrast stress echocardiography with OPTISON administration in 22 children (8 months to 19 years; mean age 9.3 ± 3.9 years) [Zilberman et al. 2003]. A dose of 0.1 mL was given for patients ≤ 25 kg, and 0.2 mL for patients > 25 kg. These doses provided adequate opacification of the LV cavity for up to 60 seconds.

Similar to the two publications, OPTISON dose in this study will be administered based on body weight. According to the Centers for Disease Control and Prevention Pediatric Growth Charts [CDC Growth Charts], children > 9 years of age usually weigh > 28 kg and children > 12 years of age usually weigh > 40 kg for both boys and girls in the United States, but weight varies greatly for a specific age. Two dose levels will be tested in each weight cohort: 0.1 or 0.2 mL per injection to children weighing ≥ 20 to ≤ 28 kg, 0.2 or 0.3 mL per injection to those who weigh > 28 to ≤ 40 kg, and 0.2 or 0.4 mL per injection to those who weigh > 40 kg. It is expected that one or more of these dose levels will be able to provide adequate LVO and EBD in these groups of pediatric patients with a limited transthoracic echocardiographic window.

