7.2 Inclusion Criteria

Subjects may be included in the study if they meet all of the following criteria:

- (1) The subject is between ≥ 9 and <18 years of age and weighs ≥ 20 kg.
- (2) The subject is clinically indicated to undergo a transthoracic echocardiogram.
- (3) The subject has a suboptimal non-contrast echocardiogram defined as ≥ 2 contiguous segments in any given view that cannot be visualized.
- (4) The subject is able to comply with study procedures.
- (5) A parent or legal guardian of the subject has signed and dated an informed consent form, and age-appropriate pediatric assent has been obtained where appropriate.
- (6) Post-menarchal female subjects must have a negative urine pregnancy test at screening and at pre-dose on the day of OPTISON administration.
- (7) Post-menarchal female subjects must be practicing abstinence, or be using an effective form of birth control (e.g., intrauterine device, oral contraceptives, contraceptive implants or injections, diaphragm with spermicide, cervical cap, or consort use of condom) for at least 30 days before being enrolled in the study.

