1 INTRODUCTION

The statistical analysis plan (SAP) defines the methods and analyses that GE HealthCare plans to use to analyze the data from Protocol GE-191-008. This SAP is based on the final study protocol (Amendment A01 Version 2.0) dated 04 October, 2022. This SAP complies with guidance promulgated by the International Conference on Harmonization (ICH) and the US Food and Drug Administration (FDA). If the protocol is subsequently amended, this SAP may be amended as well. Should the SAP and the protocol be inconsistent with respect to the planned analyses, the language of the SAP prevails.

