There are no visit windows for this study. For the statistical analyses, data will be analyzed by the nominal visit that was collected on the electronic case report form (eCRF).

Unscheduled visits will not be used in the by-visit analysis, but will be used for the following where appropriate: 1) derivations of baseline/last on-treatment measurements; 2) derivations of the maximum/minimum on-treatment values and maximum/minimum changes from baseline values for safety analyses; 3) data listings.

Definition of Missing Data Imputation

Missing values will not be substituted by estimated values but treated as missing in the statistical evaluation. Data for all enrolled participants will be presented in the data listings. A participant who is enrolled but who did not receive any amount of study drug will be included in those data listings for which they have data but will be excluded from all data summaries.

Missing or partial dates for AE or for medications may be imputed for determination of treatment emergent AE (TEAE) or concomitant medication, as follows.

- If the AE start date is completely missing, then the AE will be considered treatment emergent unless it can be determined that the AE end date/time occurred prior to IMP injection. If this is the case, the AE will not be considered treatment emergent.
- If the AE start date/time is partially missing and the partial date is not sufficient to determine if the event occurred after the IMP injection, then the AE will be considered treatment emergent unless it can be determined that the AE end date/time occurred prior to the injection.

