6.4.2 Primary Efficacy Analysis

Visualization of the 12 segments of the left ventricle wall in standard apical 4-chamber and 2-chamber views will be measured by the qualitative EBD visualization scale:

0 = no visualization of the LV endocardial border

1 = poor visualization

2 = fair visualization

3 = good/optimal visualization

Results for each segment will be summarized for non-contrast and OPTISON dose levels overall and by weight group ($\leq 40, > 40$ kg). A category “Visualized”, corresponding to scores 2 or 3, will also be presented. Additionally, the number of segments visualized (segments rated as “fair visualization” or “good/optimal visualization”) will be derived from the EBD score and summarized for non-contrast and OPTISON dose levels, overall and by weight group. 95% CI will be presented. A Paired t-test will be used to compare the number of segments visualized between non-contrast and each OPTISON dose level.

The number and percentage of subjects with an increase in the number of segments adequately visualized over non-contrast images will also be tabulated overall and by weight group for each OPTISON dose levels.

The Total LV EBD score, calculated as the sum of the individual scores assigned to each of the segment (range 0 to 36), will be tabulated overall and by weight group for non-contrast and each OPTISON dose level. The change from non-contrast to each OPTISON dose level will also be presented. 95% CI will be presented. A Paired t-test will be used to compare Total LV EBD scores between non-contrast and each OPTISON dose level.

A suboptimal echocardiogram is defined as ≥ 2 contiguous segments in any given view that cannot be visualized. The number and percentage of subjects with suboptimal echocardiogram will be presented for non-contrast and each OPTISON dose level, overall and by weight group.

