6.4.4 Handling of Uninterpretable Images

In the FAS analysis of the primary endpoint, the uninterpretable images will be categorized as none for contrast intensity and 0 visualization of EBD. In the secondary analyses, the uninterpretable images will be considered as 0 enhancement duration, poor for image quality, and non-diagnostic for diagnostic usefulness. Additionally, the number of uninterpretable images will be summarized by non-contrast and dose level.

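### SAP 6.4.3 reports LVEF as separate columns per image set with no within-child difference, although the protocol planned a comparison with non-contrast images

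*SAP*

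**What the plan says.** Protocol 12.3.2 states that LVEF "will be summarized with descriptive statistics by OPTISON dose levels and compared with non-contrast images". It does not say what form the comparison takes. SAP 6.4.3 states that LVEF "will be summarized with descriptive statistics for non-contrast and OPTISON dose levels" and stops there. The matching output, Table 14.2.9, is titled only as a summary of LVEF.

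On precedence, SAP Section 1 says: "Should the SAP and the protocol be inconsistent with respect to the planned analyses, the language of the SAP prevails". SAP Section 9 lists changes from the protocol's planned analyses, and the LVEF comparison is not among them.

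Elsewhere the SAP does use the pairing within a child. Section 6.4.2 plans paired t-tests for the number of segments visualized and for the Total LV EBD score. For the latter it adds: "The change from non-contrast to each OPTISON dose level will also be presented". Section 6.4.3 derives a contrast-minus-unenhanced change for both diagnostic confidence scores, including confidence in LVEF.

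Three further provisions bear on who would have a non-contrast value:

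- Entry (Protocol 7.2): "The subject has a suboptimal non-contrast echocardiogram defined as ≥ 2 contiguous segments in any given view that cannot be visualized".
- Missing data (SAP Section 5): "Missing values will not be substituted by estimated values but treated as missing in the statistical evaluation".
- Uninterpretable images in the secondary analyses (SAP 6.4.4): "the uninterpretable images will be considered as 0 enhancement duration, poor for image quality, and non-diagnostic for diagnostic usefulness". LVEF is given no value.

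**The concern.** Every child is imaged without contrast and at two dose levels, so each can serve as his or her own control. Reporting LVEF only as separate columns discards that pairing, and it does so for the one quantity for which the protocol had announced a comparison.

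The second problem is the denominator. Protocol 6.2.1 reports, from a cited study of children with limited windows, that "LVEF was measurable in all 20 patients using contrast echo versus only 11 with non-contrast echocardiography". If the same happens here, children without a non-contrast LVEF drop out of that column only. A difference between column means would then mix any effect of contrast with who could be measured. The gain that the cited study reported, LVEF becoming measurable at all, would appear only as a change in n.

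**Working it through.** The documents give no figure for LVEF to reproduce. The power table in SAP 2.3 concerns contrast duration and does not bear on this point.

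**Inputs**

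- Measurability: 11/20 without contrast, 20/20 with contrast (cited study, Protocol 6.2.1).
- Planned size: 30 evaluable children (SAP 2.3), reduced from about 50.
- d, the difference in true LVEF between children unmeasurable and measurable without contrast: not in the documents. Assumed 0, 3, 5 and 10 points.
- SD of LVEF: not in the documents. Assumed 10 points in both conditions.

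**Step 1: precision, even with complete data.** If all 30 children have both values, subtracting column means gives the mean within-child difference, but not its spread or confidence interval. Its standard error is 10 × √(2(1 − r)/30), where r is the within-child correlation:

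- r = 0.5: 1.83 points
- r = 0.7: 1.41 points
- r = 0.9: 0.82 points

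A reader with only the two column SDs would have to treat the columns as independent: 10 × √(2/30) = 2.58 points. The table does not supply r.

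**Step 2: possible denominators.** 11/20 = 55%, exact (Clopper-Pearson) 95% CI 31.5% to 76.9%.

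- 30 children: 30 × 0.55 = 16.5 non-contrast values; range 30 × 0.315 = 9.5 to 30 × 0.769 = 23.1, against up to 30 with contrast.
- 50 children: 27.5; range 15.8 to 38.5, against up to 50.

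**Step 3: gap in column means with no contrast effect.** Let p be the proportion measurable without contrast, and suppose all are measurable with contrast. The contrast mean is p × (mean of measurable) + (1 − p) × (mean of unmeasurable). The non-contrast mean is the mean of the measurable. The gap is therefore (1 − p) × d, in points:

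| Unmeasurable without contrast | d = 0 | d = 3 | d = 5 | d = 10 |
|---|---|---|---|---|
| 23% (upper CI limit of p) | 0 | 0.7 | 1.2 | 2.3 |
| 45% (point estimate) | 0 | 1.4 | 2.3 | 4.5 |
| 68% (lower CI limit of p) | 0 | 2.1 | 3.4 | 6.8 |

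**Step 4: cross-check with another selection model.** Let measurability depend on a normal latent score correlated ρ with LVEF (SD 10). The gap is 10 × ρ × φ(c)/p, with c the normal quantile at 1 − p. For ρ = 0, 0.3 and 0.5:

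- 55% measurable: 0, 2.2 and 3.6 points
- 75% measurable: 0, 1.3 and 2.1 points
- 90% measurable: 0, 0.6 and 1.0 points

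The gap is of the same order. It vanishes if measurability is unrelated to LVEF or if every child is measurable.

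**Step 5: the paired estimate under missingness.** With 16 pairs the standard error is 10 × √(2(1 − r)/16): 2.5, 1.9 and 1.1 points for r = 0.5, 0.7 and 0.9. Treating 16 and 30 values as independent gives 10 × √(1/16 + 1/30) = 3.1 points.

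**The case against.** The case for leaving the SAP alone has several parts.

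- **LVEF values carry little weight.** SAP 3.2 lists diagnostic confidence in LVEF as a secondary endpoint, not LVEF itself, and a within-child change is planned for that confidence. LVEF is not one of the four dose-suitability criteria. This stands and limits the severity, although SAP 6.4.3 does introduce LVEF under its secondary endpoints.
- **The protocol's comparison is unspecified and no hypotheses are tested.** Columns side by side could pass as a descriptive comparison. This stands in part: the protocol did not promise a paired estimate. But a paired difference with a confidence interval needs no hypothesis test, and the SAP goes further than that for border delineation.
- **Selective missingness is inferred.** Neither document says that a reader may leave LVEF blank. The reading rules are in the Independent Review Charter, which is not available here. A confidence scale that starts at no confidence is compatible with a value being given for every image set. This stands, so the denominator argument is conditional.
- **The cited rate may not transfer.** It comes from 20 children, and those of at least 20 kg received 0.5 mL per injection, against 0.1 to 0.4 mL here. This stands.
- **Some of the information will appear anyway.** Each summary reports n by reader, uninterpretable images are counted, and Listing 16.2.6.3 may show individual comparisons. This stands in part: none of these is a paired summary of LVEF, and an uninterpretable image is not the same thing as an unmeasurable LVEF.

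A reader might infer that the columns would describe different children and that the non-contrast mean will be biased. The documents do not support that. On the cited data the non-contrast set would be a subset of the contrast set, and bias arises only if unmeasurable children also differ in true LVEF. The documents attribute limited windows to body habitus or earlier cardiac surgery and report no link with LVEF.

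**Conclusion.** The SAP narrows the protocol's LVEF comparison to separate descriptive columns and does not record this in Section 9. That part follows from the text alone. The loss of the within-child confidence interval also holds whatever the missingness.

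The denominator problem depends on readers being allowed to leave LVEF missing. If they are, and measurability resembles the cited study, about 9 to 23 non-contrast values would stand against up to 30 with contrast. The spurious gap would be 0 if d = 0, and 1.4, 2.3 or 4.5 points at 45% unmeasurable for d = 3, 5 or 10. These values of d are illustrations, not predictions.

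It would be wrong to conclude that the dose decision is at risk, because LVEF does not enter the suitability criteria. The point concerns Table 14.2.9, a supportive result. Severity is moderate to low, and the improvement is cheap.

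**What to change.** In SAP 6.4.3 and Table 14.2.9, for each reader, add:

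- the number and percentage of children with a measurable LVEF for non-contrast and for each dose level, with a paired cross-table (measurable yes or no, non-contrast against each dose level);
- the within-child LVEF difference, dose level minus non-contrast, as a mean with 95% CI in children with both values.

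Keep the existing column statistics as descriptive, and state whether the Independent Review Charter lets a reader leave LVEF missing. If the sponsor prefers no comparison, Section 9 should record and justify dropping the protocol's.

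The cost is SAP wording and two extra table blocks from data already collected. The paired estimate may rest on fewer children (about 16 of 30 at the cited rate) and describes only those measurable under both conditions, which is why the measurability counts should stand beside it.
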